15.5 Missing, Unused and Spurious Data

No imputation will be applied for missing data. Only non-missing values will be used for analyses.

16 Study Management

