#### 6.1.3. Multiple Comparisons

Although all of the clinical efficacy analyses for this study are exploratory in nature, the ADAS-Cog 11 least square mean change from baseline analysis is considered the primary exploratory analysis of interest compared to the other clinical efficacy analyses. The primary exploratory analysis of the ADAS-Cog 11 will compare the least square mean change from baseline value for the two active arms combined to the least square mean change from baseline value for the placebo arm at day 182, using a two-sided test at the alpha=0.05 level of significance. If the primary exploratory analysis of the ADAS-Cog 11 is statistically significant, then the following comparisons will be made using the least square mean change from baseline values and the same model as for the primary analysis:

- 1) 300 mg CT1812 versus placebo;
- 2) 100 mg CT1812 versus placebo.

Each comparison will be conducted using a two-sided test at the alpha=0.05 level of significance. This fixed sequence testing procedure will control the overall level of significance for this outcome.

All other clinical efficacy analyses will be conducted using two-sided tests at the alpha=0.05 level of significance. No adjustments will be made for multiple comparisons and all other p-values will be considered nominal.

[figure not shown]

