#### 6.1.4. Handling of Dropouts or Missing Data

If a participant is missing one, two, or three individual components of the Cognitive Composite score at a time point, the Cognitive Composite score will be computed using the average of the participant's non-missing components at the time point. If a participant is missing four or more individual components at a time point, the Cognitive Composite score will not be derived at that time point.

For the interim analysis, missing data for endpoints assessed at multiple time points will be imputed using the last observation carried forward (LOCF) approach.

For the final analysis, missing data for endpoints assessed at multiple time points and analyzed using repeated measures models will not be imputed. Missing data for endpoints assessed at post baseline timepoints may be imputed using LOCF for the purpose of analyzing data using an Analysis of Covariance (ANCOVA) model when the MMRM model fails to converge.

For the interim and final analyses, missing data for endpoints assessed at only one post-baseline time point will not be imputed.

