    - If  $6 \le$  number cancellation item score  $\le 11$  then re-scale as 4
    - If  $0 \le \text{number cancellation item score} \le 5 \text{ then re-scale as } 5$ 
      - Number cancellation item scores < 0 will be re-scaled as 5
  - The resulting final number cancellation item score will range from 0 to 5.
- The ADAS-13 total score will be derived as the sum of the 13 individual items, but using the score for the number cancellation item which has been re-derived as described above.
- The ADAS-11 total score is the sum of 11 individual items excluding delayed recall and number cancellation.
- The Cognitive Composite score will be calculated using z-scores of the below items. The z-scores will be derived by calculating the baseline mean and standard deviation of each individual component for all participants. A z-score within each component will be derived for each participant at each timepoint by subtracting the corresponding baseline mean and then dividing by the corresponding baseline SD. The Cognitive Composite score will be set as the mean of the 10 individual z-scores (5 ADAS-COG scores and 5 NTB scores) within each participant and timepoint. If a participant is missing one, two, or three scores at a particular timepoint, the missing scores will be set as the average non-missing z-score of all participants at that timepoint within each component when deriving the Cognitive Composite score. If a participant is missing four or more individual components at each timepoint, the Cognitive Composite score will not be derived.
  - o ADAS-COG
    - Word recall (scored on a 0 to 10 range), average of trials I, II, and III. If at least one of the trials is missing, this component will be considered missing. The sign of the z-score for this component will be reversed when deriving the Cognitive Composite score as it is the total words not recalled that is being recorded. This test is a key measure of episodic memory.

- Orientation (0 to 8). The sign of the z-score for this component will be reversed when deriving the Cognitive Composite score as the recorded score for this test is the number of items answered incorrectly. This measure is an index of the study participant's episodic memory and a single item of semantic memory (their name).
- Delayed Word Recall (0 to 10). The sign of the z-score for this component will be reversed when deriving the Cognitive Composite score as it is the total words not recalled that is being recorded.

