#### 8.1. Composite z-scores

The composite z-scores (Cognitive Composite score; Memory Composite score; Attention Composite score; and Executive Function Composite score) defined in Section 6.1.8 will have their observed values and change from baseline summarized by visit.

Mean change from baseline within each of the four composite z-scores will be analyzed using a MMRM analysis with treatment as the main effect, visit, baseline z-score of the corresponding composite score, APOE  $\varepsilon 4$  (+ or -) status at baseline, and treatment by visit as an interaction term. All post-baseline analysis visits will be included in the model (Day 42, Day 98, and Day

182). An unstructured covariance matrix will be used to model the within-participant errors. The Kenward-Roger approximation will be used to estimate degrees of freedom.

The least squares (LS) mean change from baseline will be presented along with the associated 95% Confidence Interval (CI) within each treatment group. In comparing treatments (CT1812 100 mg/day minus placebo, CT1812 300 mg/day minus placebo, and the CT1812 groups combined versus placebo), LS mean differences in change from baseline will be presented along with associated 95% CIs and pairwise treatment *P*-values.

In the case of convergence issues, other covariance structures will be considered including (but not limited to) Toeplitz, compound symmetry (CS) and autoregressive (AR[1]) with each model fit to find the covariance structure with the best fit. The fit statistics will be compared for all covariance structures and the structure with the smallest Akaike information criterion will be retained as the preferred model.

For the interim analysis, ANCOVA model at each visit will be run in place of the MMRM. This model will include treatment as the main effect, baseline z-score of the corresponding composite scores, and APOE  $\varepsilon 4$  (+ or --) status at baseline. For endpoints where LOCF is used, the analyses will be repeated using only observed data.

The composite z-scores will also be listed.

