#### 10. Changes from Planned Analysis

Four additional analysis populations are defined in this SAP but are not defined in the study protocol: All Subjects Population, mITT Population, Completers Population, and PK Population. These analysis populations have been added to enable the summary of disposition, the primary analysis of efficacy data (mITT), a sensitivity analysis of efficacy data (Completers), and analysis of PK data (PK). The Per-Protocol Population, also not defined in the study protocol but included in V1.0 of the SAP, was removed.

The score for the number cancellation item was originally set up to be derived within the clinical

study database, however prior to database lock, an error was discovered in the derivation of this item score. This error subsequently impacts the derivation of the ADAS-13 total score, which was also originally set up to be derived within the clinical study database. As a result, both the number cancellation item score and the ADAS-13 total score will be re-derived in the ADaM datasets for analysis purposes.

The Modified Hachinski total score and ADCS-ADL total score were originally calculated and entered into the study database by the sites. To ensure accuracy, it was decided to re-derive these total scores in the ADaM dataset.

Composite z-score scales (Cognitive Composite score; Memory composite score; Attention composite score; Executive Function composite score) are added to efficacy endpoints and their derivation are included in Section 6.1.8.

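### SAP 6.1.4 and 6.1.8 give two different Cognitive Composite scores when one to three components are missing, and nothing says which rule governs

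*SAP*

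**What the plan says.** The Cognitive Composite is the mean of ten z-scores, five from the ADAS-Cog and five from the NTB. On standardisation, SAP 6.1.8 says: "The z-scores will be derived by calculating the baseline mean and standard deviation of each individual component for all participants".

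Two sections then deal with partly missing components:

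- **SAP 6.1.4 (dropouts and missing data).** The trigger is "If a participant is missing one, two, or three individual components of the Cognitive Composite score at a time point". The score is then the average of the participant's "non-missing components at the time point". Nothing is filled in.
- **SAP 6.1.8 (derived variables).** The trigger is the same, one to three missing scores at a timepoint. Here "the missing scores will be set as the average non-missing z-score of all participants at that timepoint within each component", and the composite is the mean of all ten values.

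Both sections leave the score underived when four or more components are missing.

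Two other sections point to 6.1.8. SAP 8.1 says the composites "defined in Section 6.1.8 will have their observed values and change from baseline summarized by visit". SAP 10 says the composite scales "are added to efficacy endpoints and their derivation are included in Section 6.1.8". Neither mentions missing components or 6.1.4. Protocol 15.5 rules out imputation and adds: "Only non-missing values will be used for analyses".

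**The concern.** The trigger and the score are the same, but the answers differ. One rule uses only the participant's own data. The other brings in the average of everyone else's data, pooled over arms. They cannot be read as a single rule, so two programmers who each follow the SAP could produce different analysis datasets.

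The composite is a listed efficacy endpoint. It enters the MMRM as both outcome and baseline covariate, and it feeds the figures, the descriptive summaries and the biomarker correlations. Gaps are also easy to trigger, because one missing Word Recall trial makes that whole component missing. An unresolved rule leaves a choice that could be made after results are seen, in a document that describes itself as an a priori plan.

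**Working it through.** The plan states no figure to reproduce here, so the check compares the two rules algebraically.

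**Notation.** k = number of missing components (1 to 3 of 10); s = mean z of the participant's observed components; F = mean of the all-participant values filled in. The documents give no component-level data or missingness rate, so every value of s, F and p below is an assumption.

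**Score for one participant**

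- 6.1.4: s
- 6.1.8: [(10 − k)s + kF]/10
- Difference (6.1.8 minus 6.1.4): (k/10)(F − s), which is zero only if F = s

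At the analysis baseline F = 0, because the z-scores are centred on the all-participant baseline mean. After baseline, F is the average drift on the missing tests.

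| s | F | k | 6.1.4 | 6.1.8 |
|---|---|---|---|---|
| −1.0 | 0 | 1 | −1.00 | −0.90 |
| −1.0 | 0 | 2 | −1.00 | −0.80 |
| −1.0 | 0 | 3 | −1.00 | (−7.0 + 0)/10 = −0.70 |
| −1.0 | −0.3 | 3 | −1.00 | (−7.0 − 0.9)/10 = −0.79 |

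**False change from baseline.** Take a participant at −1.0 on every test at both visits, with three tests missing only after baseline and F = −0.1. Under 6.1.4 the change is 0.00. Under 6.1.8 the later score is (−7.0 − 0.3)/10 = −0.73, a change of +0.27.

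**Treatment contrast, balanced random missingness.** Let a fraction p in each arm miss k components, with a uniform effect δ on all tests. The active mean is (1 − p)δ + p[((10 − k)/10)δ + (k/10)F] and the placebo mean is p(k/10)F. F cancels, leaving δ(1 − pk/10). With δ = 0.30:

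- 20% miss one: 0.30 × 0.98 = 0.294
- 10% miss three: 0.30 × 0.97 = 0.291
- 20% miss three: 0.30 × 0.94 = 0.282

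A simulation of the last case (300,000 participants, 2:1 allocation, inter-test correlation 0.5, baseline-adjusted) gave 6.1.8 against complete-data contrasts of 0.2816 against 0.3000 at between-visit correlation 0.7, and 0.2845 against 0.3024 at 0.9. Both ratios are about 0.94, as the formula predicts.

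**Treatment contrast, unbalanced missingness.** The two rules' unadjusted contrasts differ by (k/10)[pA(F − sA) − pP(F − sP)], with A for active and P for placebo. With s = −1.0 in both arms, F = 0 and k = 3:

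- 10% active, 5% placebo: 0.3 × 0.05 = +0.015
- Arms swapped: −0.015
- 20% active, 10% placebo: 0.3 × 0.10 = +0.030

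**When the missing test is atypical for the person.** Nine tests are at −1.0, there is no true change, the tenth test is missing only at Day 182, and F = 0.

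| Tenth test | True score | 6.1.4 (false change) | 6.1.8 (false change) |
|---|---|---|---|
| −2.5 (e.g. TMT B) | (−9.0 − 2.5)/10 = −1.15 | −1.00 (+0.15) | −0.90 (+0.25) |
| +1.0 | (−9.0 + 1.0)/10 = −0.80 | −1.00 (−0.20) | −0.90 (−0.10) |

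**The case against.** The textual conflict is not in dispute. The case on the other side concerns its weight and the choice of remedy.

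- **The effect is small against sampling error.** This stands. With inter-test correlation 0.5 the composite SD is √[(1 + 9 × 0.5)/10] ≈ 0.74. With 48 per arm less 15% dropout (40.8 placebo, 81.6 pooled active), the unadjusted SE is 0.74 × √(1/81.6 + 1/40.8) ≈ 0.14. It falls to about 0.10 or 0.06 after adjustment for a baseline correlated 0.7 or 0.9. The largest balanced shift above, 0.018, is thus roughly 0.13 to 0.29 SE. The unbalanced shifts of 0.015 and 0.030 are about 0.11 and 0.21 of the unadjusted SE.
- **The pointers in 8.1 and 10 favour 6.1.8.** They do, as the place of definition. But 6.1.4 is the missing-data section, names this score, and says that repeated-measures endpoints are not imputed at the final analysis.
- **The 6.1.8 fill has a merit.** It is specific to component and visit, so it keeps the ten-test mix and carries the missing test's average drift. That is true, and the +1.0 example shows 6.1.4 doing worse. Neither rule is bias-free.
- **Protocol 15.5 is weak support.** It does not address composite scoring, the SAP added the composites itself, and the SAP already departs from 15.5 with LOCF. It is therefore a supporting reason only.
- **F need not be exactly zero at baseline.** If the fill used Day 1 values alone while the centring mean included screening values for people with a Day 1 gap, F could differ slightly from zero. On the analysis baseline as defined in SAP 6.1.1 it is zero.
- **The interim has already been planned unblinded.** Part A data are analysed unblinded and re-enter the final analysis, so the choice is not fully blind. The sponsor should say which rule was used there.

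**Conclusion.** The SAP contradicts itself. For one to three missing components it prescribes two scores, and no text ranks them. For an affected participant the gap can reach 0.30 z units (s = −1.0, F = 0, k = 3). On the arm contrast, the all-arm fill shrinks a uniform effect by the factor 1 − pk/10 under balanced random missingness. If missingness differs by arm, it can move the contrast slightly either way. The assumed rates used here give shifts of 0.006 to 0.030, and the real size cannot be determined from the documents.

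The reach is limited. Only participants with one to three gaps are affected, on one exploratory endpoint for which, under SAP 6.1.3, "all other p-values will be considered nominal". ADAS-Cog 11 is untouched. So are the Memory, Attention and Executive Function composites, which are not derived if any item is missing. The point should be corrected, but it does not threaten the trial's main conclusions.

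**What to change.** Before database lock and final unblinding, keep one rule and state it consistently.

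- **Recommended text.** Delete the all-participant-mean sentence from SAP 6.1.8. Replace it with a cross-reference to the 6.1.4 rule: with one to three missing, average the participant's own observed components; with four or more missing at that time point, do not derive the score. Apply this at baseline and after. The cross-reference belongs in 6.1.8 because 8.1 and 10 send the reader there.
- **Tidy in the same edit.** Align the four-or-more wording in 6.1.8, which speaks of each timepoint, with 6.1.4, which speaks of a single time point. State which rule the interim analysis used.
- **Limitation to record.** The person-mean rule can mislead when the missing test is atypical for that participant.
- **Reporting.** Give the number of participants with one to three missing components by arm and visit.

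The reasons for 6.1.4 are that it uses only the participant's own data, has no pull toward the all-arm mean, and fits the SAP's final-analysis no-imputation text. A sponsor who prefers 6.1.8 must still amend 6.1.4.

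The cost is one sentence deleted, one cross-reference added and one count table. If programs already follow 6.1.8, the derivation code and its checks change as well.

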#### 6.1.8. Derived Variables

- Change from baseline = value at current time point value at baseline.
- Treatment-emergent AE (TEAE) = any AE with an onset date/time on or after the first dose of study drug.
- Modified Hachinski total score = the sum of the individual 8 item scores. Items 1, 6, 7 & 8 attract a score of 2-points if present (range of 0-8). Items 2, 3, 4 & 5 attract a score of 1-point if present (range of 0-4). The total score ranges from 0 12.
  - The sites were originally responsible for manually calculating the total score and entering it into the clinical study database. To ensure accuracy, it was decided to re-derive this total score in the ADaM dataset.
- ADCS-ADL total score = the sum of the individual 23 item scores. The score ranges from 0-78.
  - The sites were originally responsible for manually calculating the total score and entering it into the clinical study database. To ensure accuracy, it was decided to re-derive this total score in the ADaM dataset
- The ADAS-13 total score = the sum of all 13 individual items (word recall; commands; constructional praxis; delayed word recall; naming objects and fingers; ideational praxis; orientation; word recognition; remembering test instructions; spoken language; word finding; comprehension of spoken language; and number cancellation).
  - The score for the number cancellation item was originally set up to be derived within the clinical study database, however prior to database lock, an error was discovered in the derivation of this item score. This error subsequently impacts

the derivation of the ADAS-13 total score, which was also originally set up to be derived within the clinical study database.

- As a result, both the number cancellation item score and the ADAS-13 total score will be re-derived in the ADaM dataset for analysis purposes as follows:
- The number cancellation score will be derived in two steps:
  - Step 1: Calculate the preliminary number cancellation item score as (number of targets hit) – [(number of errors) + (number of times to remind to task)]
  - Step 2: Take the preliminary number cancellation item score calculated in Step 1 and re-scale as follows:
    - If number cancellation item score is > 30 then re-scale as 0
    - If  $24 \le$  number cancellation item score  $\le 29$  then re-scale as 1
    - If  $18 \le$  number cancellation item score  $\le 23$  then re-scale as 2
    - If 12 < number cancellation item score < 17 then re-scale as 3

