- Word Recognition (0 to 24). The sign of the z-score for this component will be reversed when deriving the Cognitive Composite score. This is a further test of episodic memory using a word recognition paradigm of 12 true positive targets and 12 foil items. While the possible score for this measure is 0 to 24, the standard ADAS-Cog score is capped at a maximum worst score of 12.
- Number Cancellation (raw score 0 to 40, subsequently re-scaled to a 5-point scale [0-5]). In this task, the participant is asked to cross off as many target digits as possible in 45 seconds. The score is derived as the number of incorrectly crossed-off items and the number of reminders given subtracted from the number of items correctly crossed off. The resulting score (0-40) is then re-scaled to a 5-point scale (0-5) as described earlier in this section. NTB
  - COWAT This test of working memory and executive function yields a key metric referred to as 'Total number of acceptable words'. This is obtained by calculating how many of the study participant's responses are deemed acceptable according to the scoring rules. The total score for COWAT is the sum of the number of accepted words for each of the 3 tests (three letters). The score range for this test is typically between 0 and 80, though floor performance (a score of 0) is vanishingly rare in mild-to-moderate stage AD participants.
  - CFT This is a further test of working memory and executive function that yields a key metric referred to as 'Total number of acceptable words'. This is obtained by calculating how many of the study participant's responses are deemed acceptable according to the scoring rules. The usual performance range for this test is between 0 and 40.
  - Digit Span This is a brief measure of working memory, especially in the Digits Backwards section. The key metric is 'Total number of trials correct', which is the number of sequences correctly recalled. The range of the test is 0 to 24 and both floor and ceiling effects are rare.
  - Trail Making Test (TMT) A This is essentially a measure of attention, as successful completion relies on quickly and accurately connecting numbered circles in an ascending sequence. The key metric for analysis

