purposes is 'Time taken for completion'. Errors and time taken once again both contribute to performance. However, because errors incur a time penalty, it is not necessary to analyze both metrics. The sign of the z-score for this component will be reversed when deriving the Cognitive Composite score.

- Trail Making Test (TMT) B This is the more complex component of the TMT in which successful completion relies on the study participant accurately connecting the numbered and lettered circles. Study participants are required to alternate between numbers and letters in an ascending sequence. The key metric for analysis purposes is again 'Time taken for completion'. As with TMT A, because errors incur a time penalty, it is not necessary to factor in errors for analysis purposes. The sign of the z-score for this component will be reversed when deriving the Cognitive Composite score.
- The Memory composite score will be a composite z-score average similar to the Cognitive Composite score but will only be derived using the average of the ADAS-Cog Word Recall, Orientation, Delayed Word Recall, and Word Recognition items. If a participant is missing any of the four items at a timepoint, this composite score will not be derived.
- The Attention composite score will be a composite z-score average derived using the average of the Number Cancellation and TMT A items. If a participant is missing either of the two items at a timepoint, this composite score will not be derived.
- The Executive function composite score will be a composite z-score average derived using the average of the COWAT, CFT, Digit Span, and TMT B items. If a participant is missing any of the four items at a timepoint, this composite score will not be derived.

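### The re-scaled Number Cancellation item runs higher = worse but gets no sign reversal, so the Attention composite can cancel or invert and the Cognitive Composite moves the wrong way on this item

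*SAP*

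**What the plan says.** All of the scoring text is in SAP 6.1.8.

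- **Re-scaling.** Number Cancellation is first scored as targets hit minus errors and reminders, then re-scaled in bands. At the top, "If number cancellation item score is > 30 then re-scale as 0". At the bottom, raw scores from 0 to 5 become 5, and "Number cancellation item scores < 0 will be re-scaled as 5". The text treats this 0-5 value as the final item score.
- **Component entry.** In the list of Cognitive Composite components, Number Cancellation is described as a raw 0-40 score, and the description closes with "The resulting score (0-40) is then re-scaled to a 5-point scale (0-5) as described earlier in this section". No sign instruction follows.
- **Reversals.** Word Recall, Orientation, Delayed Word Recall, Word Recognition, TMT A and TMT B each carry a reversal. For Word Recognition and both TMT parts the sentence is "The sign of the z-score for this component will be reversed when deriving the Cognitive Composite score". The other three are tied to the Cognitive Composite in the same way.
- **Sub-composites.** Attention is the "average of the Number Cancellation and TMT A items". Executive Function is the "average of the COWAT, CFT, Digit Span, and TMT B items". Neither definition has a sign rule. Memory is "a composite z-score average similar to the Cognitive Composite score but will only be derived using" its four ADAS-Cog items.
- **Use.** SAP 8.1: "Mean change from baseline within each of the four composite z-scores will be analyzed using a MMRM analysis". SAP 8 adds figures for each composite, and SAP 8.9 correlates all four with the biomarkers.

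**The concern.** A composite of z-scores can be interpreted only if every component points the same way. Six of the seven components that are higher = worse (counting the 0-5 Number Cancellation score) are turned round, and Number Cancellation is not. In a ten-item average one wrong sign dilutes the result. In a two-item average it decides the result.

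Attention is a listed efficacy endpoint with treatment differences, confidence intervals and p-values. A programmer who follows the text could produce an Attention score on which a real benefit appears as no effect or as harm. Two competent programmers could also produce scores of opposite sign. If the sign is settled only once treatment results are visible, the choice is no longer pre-specified.

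**Working it through.** The plan gives no effect size or power for the composites, so there is no figure of its own to reproduce. The sign result needs only the definitions. The power figures need assumptions, which are marked.

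**1. Direction of the item.** In SAP 6.1.8 the bands give 0 for raw scores above 30, then 1, 2, 3 and 4 as the raw score falls, and 5 for the lowest and all negative scores. The 0-5 score falls as performance improves, so it is higher = worse.

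**2. Attention.** Let *a* be the true benefit on TMT A and *b* the true benefit on Number Cancellation, in SD units, with positive meaning better. The composite is the mean of two z-scores.

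| Score z-scored | TMT A reversal carried over? | Attention effect | a = b = 0.3 |
|---|---|---|---|
| 0-5 | yes | (a - b)/2 | 0 |
| 0-5 | no | (-a - b)/2 | -0.3 |
| raw 0-40 | no | (b - a)/2 | 0 |
| raw 0-40 | yes | (a + b)/2 | +0.3 |

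Only the last row is correct. It needs two things the SAP does not state. A simulation that put raw scores through the actual bands (assumed raw mean 18 and SD 7, correlation 0.3 to 0.7, benefit 0.3 SD) gave +0.01, -0.29 to -0.30, 0.00 and +0.30 for the four rows.

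**3. Cognitive Composite.** With the 0-5 score unreversed and an equal benefit *d* on all ten components, the mean effect is (9d - d)/10 = 0.8d. For d = 0.3 this is 0.24 instead of 0.30. A 1 SD improvement on Number Cancellation alone moves the composite by -0.10 instead of +0.10.

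**4. Illustrative power.** The protocol and SAP plan 48 per group with 15% dropout: 96 x 0.85 = 81.6 and 48 x 0.85 = 40.8, so 82 (pooled CT1812) v 41 (placebo), df = 82 + 41 - 2 = 121, two-sided alpha 0.05, noncentral t. Assumptions not in the documents: d = 0.3, unit-SD change scores, and a common inter-item correlation rho.

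*Attention*, first row of the table: SD = sqrt((1 - rho)/2). Sign-aligned: SD = sqrt((1 + rho)/2).

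| rho | Power, sign-aligned | Power, 0-5 unreversed and TMT A reversed |
|---|---|---|
| 0 | 59.5% | 5.0% |
| 0.2 | 51.9% | 5.0% |
| 0.3 | 48.8% | 5.0% |
| 0.5 | 43.5% | 5.0% |

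With unequal effects (a = 0.15, b = 0.30), the estimate is (0.15 - 0.30)/2 = -0.075 instead of (0.15 + 0.30)/2 = +0.225. Power is 8.5% (rho 0) to 12.2% (rho 0.5), of which 7.9 to 11.9 points are significant results favouring placebo. Sign-aligned power is 37.9% to 27.1%.

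*Cognitive Composite.* One wrong sign also changes the SD of the average. The SD ratio is 1.000, 0.862 and 0.820 at rho 0, 0.2 and 0.5, so the standardised effect ratio is 0.8/1.000 = 0.80, 0.8/0.862 = 0.93 and 0.8/0.820 = 0.975. Power, aligned v unreversed:

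| rho | Aligned | Unreversed |
|---|---|---|
| 0 | 99.8% | 97.6% |
| 0.1 | 94.6% | 88.7% |
| 0.2 | 83.7% | 77.9% |
| 0.3 | 72.5% | 68.2% |
| 0.5 | 55.5% | 53.4% |

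**5. Executive Function, strictly literal reading.** If the TMT B reversal applies only to the Cognitive Composite, the mean effect is (3d - d)/4 = 0.5d. The standardised ratio is 0.50, 0.63 and 0.79 at rho 0, 0.2 and 0.5.

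**The case against.** The strongest reply is that the raw 0-40 score was meant. The component entry names it first. A raw score is higher = better and needs no reversal, and the direction of the other nine components is handled correctly, so the missing sentence may be deliberate. The neighbouring Word Recognition entry gives a 0-24 range and notes that the standard ADAS-Cog score is capped at 12, which suggests the composites may use finer metrics than the ADAS total. The re-scaling was also introduced to repair the ADAS-13 total.

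This stands as a possible reading, and on it the Cognitive Composite is right. It does not settle the matter. The entry's last scoring step is the 0-5 score, the text treats that as the final item score, and only the re-scaling step deals with negative raw values. Even with the raw score, Attention is right only if the TMT A reversal, stated for the Cognitive Composite, is assumed to carry over.

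Two further objections have some force. One set of signed z-scores feeding all four composites is a reasonable expectation, so Executive Function is a worst case and Memory, described as similar to the Cognitive Composite, needs only confirmation. The power figures rest on assumed effects and correlations, while the SAP scales by baseline SD and uses an MMRM with baseline and APOE terms. They show scale only. Exact cancellation also needs equal effects; with unequal effects the items partly offset, possibly with the wrong sign.

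**Conclusion.** The concern holds, on the condition that the 0-5 score is z-scored, which is the natural reading but is not stated outright. On that reading Attention is either the difference of its two items or an inverted scale, and the Cognitive Composite carries one component in the wrong direction. These sign results do not depend on rho or on any assumed sample size. The loss is severe for Attention and modest for the Cognitive Composite (0.8 of the mean effect for equal benefits; about 2 to 6 points of power under the stated assumptions).

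The scope is limited. SAP 10 records that the composites were added by the SAP. All efficacy is exploratory (SAP 8) and these p-values are nominal (SAP 6.1.3). The composites are not in the Completers sensitivity analysis, and SAP 8.1 gives no subgroup analysis for them. NTB components are modelled separately (SAP 8.4) and the Cognitive Composite components are summarised (SAP 8.7), so a reversed direction could be noticed. ADAS-Cog 11 excludes the item, and in ADAS-13 its 0-5 direction is correct. It should be fixed, but it does not threaten the trial's main conclusions.

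**What to change.** Make two additions to SAP 6.1.8:

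1. In the Number Cancellation entry, state either that the 0-5 score is z-scored and its sign reversed, or that the raw 0-40 score is z-scored without reversal.
2. State once that the same sign-aligned component z-scores, with higher meaning better, are used in the Cognitive, Memory, Attention and Executive Function composites.

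Document both before the final unblinding and check the program against them. The cost is two sentences and a one-line programming change; no new data are needed.
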